6 SUBJECT DISPOSITION

The number of subjects who are in the intent-to-treat (ITT) population, who are in the full analysis set (FAS) population, who are in the safety population, who complete the study, and who discontinue from the study, along with reason of study discontinuation, will be summarized in tabular format for the ITT population. Subject disposition information will be displayed for the ITT population in a subject listing.

7 DEMOGRAPHIC CHARACTERISTICS

For quantitative variables (e.g., age, height, weight, BMI), summary statistics (n, mean, standard deviation, minimum, median, and maximum) will be presented for all subjects in the safety population. For qualitative variables (e.g., sex, race, ethnicity), results will be summarized for all subjects in the safety population as counts and percentages. Individual demographic information for the safety population will be displayed in subject listings.

8 MEDICAL HISTORY

Medical history findings will be coded using the Medical Dictionary for Regulatory Activities (MedDRA) coding system (using MedDRA Version stated in Data Management Plan). Medical history findings will be summarized by System Organ Class and Preferred Term. Individual medical history findings will be listed for the safety population.

9 PHYSICAL EXAMINATION

Abnormal physical examination findings will be listed for the safety population.

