11.3 Ophthalmologic Examination

A full medical eye examination including fundus photographs of the posterior pole of eye, OCT of the maculas of both eyes, and slit lamp evaluations will be performed at screening and at the completion of dosing (approximately Day 61) to characterize the subject's baseline status and to monitor any changes from baseline over the course of treatment. Pupillary dilation will be accomplished with 2.5% neosynephrine and 0.5% tropicamide (Mydriacyl) (unless there is a contraindication deemed by the ophthalmologist), one drop in each eye one time in light color eyes and up to two times, 5 minutes apart in dark eyes. A slit lamp is a biomicroscope with a bright light used during an eye exam and assesses different structures at the front of the eye and inside the eye for determination of the health and detection of eye disease. OCT is a non-invasive imaging technique that uses light waves to take cross-section pictures of the retina. Fundus photography involves photographing the rear of the eye. These procedures are standard tests involved in the medical evaluation of the health of the eye and should be conducted by a limited number of coordinating ophthalmologists to ensure consistency of evaluations.

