4.2 Secondary Endpoints

Pharmacodynamics

• Change from baseline in body weight at Day 61.

- Change from baseline in whole body adiposity at Day 61 [i.e., total visceral adipose tissue (VAT) and subcutaneous adipose tissue (SAT)]
- Changes from baseline in surrogate measures of liver inflammation and fibrosis at Day 61: Fibroscan® Vibration-controlled Transient Elastography (VCTE), Fibroscan® Controlled Attenuation Parameter (CAP) score, and Enhanced Liver Fibrosis (ELF) score.
- Change from baseline in lipid parameters and cardiovascular risk biomarkers at Day 61: serum high sensitivity C-reactive protein (hs-CRP), Lp(A), Apo B, low-density lipoprotein (LDL), high-density lipoprotein (HDL), total cholesterol, triglycerides, and free fatty acids (FFA).
- Change from baseline in metabolic disease parameters at Day 61: homeostatic model assessment for insulin resistance (HOMA-IR), fasting blood glucose concentrations, glycated albumin concentrations, HbA_{1c}.

Safety and Tolerability

- Summary of physical examinations findings over the course of the study.
- Adverse event (AE) assessment over the course of the study.
- Assessment of vital sign parameters over the course of the study, including resting systolic and diastolic blood pressure, resting heart rate, resting respiratory rate, and oral body temperature.
- Assessment of body weight over the course of the study.
- Safety 12-lead electrocardiograms (ECGs) over the course of the study.
- Assessment of clinical laboratory values (hematology, full biochemistry panel (including lipid panel, creatinine phosphokinase (CPK), magnesium, liver function tests, and urinalysis over 61 days of dosing.
- Assessment of ophthalmologic examination, including slit lamp, prior to and after 61 days of dosing.

Pharmacokinetics

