15 SUBJECT LISTINGS

Data that are collected and entered into the study database but that are not displayed in the summary tables that are specified in the preceding sections will be presented in subject listings. These will include (but will not be limited to) data from the following modules:

Dosing Information

Inclusion/Exclusion Criteria

Protocol Deviation

Neurological Examination

[figure not shown]
Ophthalmology Examination

Concomitant Procedures

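### Two named safety endpoints and the muscle-strength grades get listings only: no examination-based incidence or shift by arm is planned

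*SAP*

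**What the plan says.** SAP 4.2, in agreement with Protocol 5.2.2, includes among the safety and tolerability endpoints "Summary of physical examinations findings over the course of the study" and "Assessment of ophthalmologic examination, including slit lamp, prior to and after 61 days of dosing". Protocol 11.3 says that the eye examination (slit lamp, OCT of the maculas, fundus photographs) serves to characterize baseline and "to monitor any changes from baseline over the course of treatment". Protocol 11.2 makes strength testing part of both the complete and the targeted physical examination and sets out a 0 to 5 grading scale. The schedule in Protocol 8.1 places these examinations at screening and at Days 1, 14, 28, 42, 61 and 73.

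On output, SAP 9 consists of one sentence: "Abnormal physical examination findings will be listed for the safety population". SAP 15 states that data "not displayed in the summary tables that are specified in the preceding sections will be presented in subject listings", and its list of such modules includes "Neurological Examination" and "Ophthalmology Examination". SAP 13 has no subsection for any of the three examinations. Protocol 12.3.4 describes summaries of adverse events, laboratory values, vital signs and ECG intervals, and none for these examinations.

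**The concern.** A listing by subject is not a summary, so the output for physical examination does not deliver the endpoint as worded. The eye endpoint is defined by two time points, yet no analysis of change between them is planned. Strength is graded repeatedly, and nothing counts the subjects whose grade falls.

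With up to 80 subjects in four arms, a listing leaves the reader to work out which abnormalities are new, in which arm, and out of how many subjects examined. Safety and tolerability form one of the two primary objectives (SAP 3). For these endpoints the report would have no rate, no view across doses and no upper bound when nothing is seen, except where a finding was reported as an adverse event.

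**Working it through.** **Endpoint against output**

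| Domain | What is promised or collected | Planned output from the examination |
|---|---|---|
| Physical examination | Endpoint worded as a summary over the study (SAP 4.2) | Listing of abnormal findings (SAP 9) |
| Ophthalmology | Endpoint before and after dosing (SAP 4.2); purpose is to monitor change (Protocol 11.3) | Listing (SAP 15) |
| Neurological examination, including strength | 0 to 5 grades within the physical examination (Protocol 11.2); not a separately named endpoint | Listing (SAP 15) |

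None of the three has a count or shift by arm. Elsewhere the SAP does provide such tables. Neutrophil count gets a shift table (SAP 13.2), QTcF gets categories of concern (13.5), and medical history is summarized by class and term (SAP 8). PEth, which is not a named endpoint, gets summary statistics at each time point (13.2).

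**What the adverse event tables cover**

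1. Protocol 11.7.1 makes examination findings judged clinically significant by the investigator a source of adverse events.
2. SAP 13.1 tabulates all treatment-emergent events by class and term, and SAP 5.2 makes summaries by treatment group. A clinically significant new eye or strength finding is therefore counted by arm.
3. A new OCT or lens change, or a fall in strength from 5 to 4, that is judged not significant is not counted.
4. The event tables use the safety population, that is, everyone dosed. Zero eye events does not show that everyone was examined twice and found unchanged. Only a table of subjects with both examinations gives that denominator.

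**What a paired table could say**

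The documents give no figure for these outputs and no expected rate of findings. The inputs are the planned 20 per arm (SAP 2) and the 15% dropout (SAP 5.3). The plan's own counts reproduce: 4 × 17 = 68 and 68 / 0.85 = 80, or 20 per arm. Three HU6 arms give 3 × 20 = 60 subjects, or 3 × 17 = 51 after dropout. Eighty subjects give at most 80 before/after pairs of eye examinations (about 160 examinations), and about 68 pairs if 15% lack the second.

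For zero events in n subjects, the exact two-sided 95% upper limit is 1 − 0.025^(1/n):

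| Denominator | Upper limit |
|---|---|
| 0/20, one arm | 16.8% |
| 0/60, pooled HU6 | 6.0% |
| 0/17, one arm, 15% without a second examination | 19.5% |
| 0/51, pooled HU6, 15% without a second examination | 7.0% |

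The chance that an arm of 20 shows at least one case is 1 − (1 − p)^20: 33%, 64%, 88% and 96% for assumed true rates of 2%, 5%, 10% and 15%. Small arms would thus often contain something to tabulate if the rate were 5% or more.

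**The case against.** The strongest answer is the adverse event route: anything the investigator thinks matters is already tabulated by arm. That stands, and it limits the point. A reader might infer from SAP 9 and SAP 15 that no incidence by arm will exist for eye or strength harms. The documents do not support that reading. What is missing is the examination-based table, chiefly for changes below the adverse event threshold and for the number examined at both times.

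A reader might also infer that these examinations target known toxicities of HU6. The public text does not say so: the Introduction is omitted, Protocol 11.3 gives only the general purpose of monitoring change, and Protocol 11.2 gives no drug-specific reason for strength testing. The point does not need that inference.

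It can also be said that SAP 5.2 allows tables and/or listings, that Protocol 12.3.4 requires no table here, and that this is an exploratory Phase 2a study. All true, so the SAP does not depart from the protocol's analysis section. But a general permission to list does not turn a listing into the summary named as an endpoint, nor does it supply a before/after comparison.

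The tables would not support tests. A pattern of 3/20 against 0/20 has a two-sided Fisher p of 2 × C(20,3)/C(40,3) = 2 × 1140/9880 = 0.23. Their use is descriptive.

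Finally, the case report form is not in the documents, Protocol 11.2 names no specific muscles, and the targeted examination is symptom-based. This stands, so the tables should use the categories actually recorded.

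**Conclusion.** The point holds in limited form. Two endpoints named in SAP 4.2, and the repeated strength grades, have no planned summary from the examinations themselves. Clinically significant findings reported as adverse events remain visible by arm. The loss is the count of lesser new or worse findings and the paired denominator, and with it the upper limits shown above. The limits for 20 and 60 assume that every subject has both examinations; those for 17 and 51 assume that the planned dropout rate applies to the second examination. This is a low-cost improvement to safety reporting; it does not affect the efficacy analysis.

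**What to change.** Keep the listings. Add to SAP 9 and SAP 13 three descriptive tables in the safety population, by arm and for pooled HU6, using the categories recorded on the case report form:

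1. n (%) with new or worsened abnormal physical findings.
2. A shift table of eye findings from screening to Day 61 or early termination, among subjects with both examinations, showing that number and the exact 95% interval for new or worse findings.
3. n (%) with any fall in recorded muscle-strength grade from baseline.

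Remove the neurological and ophthalmology modules from the SAP 15 list of data without a table. The eye table should also state which early-termination examinations count. Protocol 8.1 marks that examination only for subjects with at least 28 days of dosing, while Protocol 8.2.11 also includes subjects below 28 days who have been dosed for at least 14; these passages need to be reconciled.

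The cost is SAP wording and modest programming on data already scheduled for collection. Sample size and alpha stay as they are. Rewording the endpoints to match the listings would also remove the mismatch, but would leave the safety objective less well reported.

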10 PRIOR AND CONCOMITANT MEDICATIONS

Medications will be coded using World Health Organization Drug Dictionary (WHODRUG, version specified in the Data Management Plan). Prior medications and concomitant medications will be summarized separately by Anatomical Therapeutic Chemical (ATC) Level 4 term and Preferred Name. Prior medications are defined as medications taken prior to the first dose of study drug, including those medications that were continued during the study. Concomitant medications will be defined as medications started after the first dose of study medication. Individual medications will be displayed in subject listings.

11 EFFICACY ANALYSES

The primary efficacy endpoint will be the reduction in liver fat content measured by the relative change from baseline, as assessed by MRI-PDFF at Day 61. The hypotheses of interest are 2-sided tests comparing each active HU6 treatment group to the placebo group.

```
\begin{split} H_{01} \colon & \mu_{placebo} = \mu_{HU6 \; 150mg} \text{vs} \; H_{11} \colon \mu_{placebo} \neq \mu_{HU6 \; 150mg} \\ & H_{02} \colon \mu_{placebo} = \mu_{HU6 \; 300mg} \text{vs} \; H_{12} \colon \mu_{placebo} \neq \mu_{HU6 \; 300mg} \\ & H_{03} \colon \mu_{placebo} = \mu_{HU6 \; 450mg} \text{vs} \; H_{13} \colon \mu_{placebo} \neq \mu_{HU6 \; 450mg} \end{split}
```

Summary statistics (n, mean, standard deviation, minimum, median, and maximum) will be presented for the observed values for MRI-PDFF at each time point for the FAS population, as described in Section 5.2, Summarization of Data. Summary statistics will also be presented for the change-from-baseline values to each postbaseline time point as well as placebo-corrected change-from-baseline values to each postbaseline time point. In these displays, baseline will be defined as the last non-missing value prior to first dose of study medication. Figures will be generated appropriate to the data output.

Mean change from baseline in liver fat content will be analyzed for the FAS population using an analysis of covariance (ANCOVA) model, including treatment group, HbA_{1c} stratification (normal range versus between 5.7% and 9.0% inclusive) and baseline liver fat from MRI-PDFF as fixed effects. This estimand will include available MRI-PDFF evaluations that occur before discontinuation of treatment. The difference in LS Means for the change from baseline, corresponding 95% CIs, and P values will be provided to assess the treatment differences between placebo and each HU6 treatment group. A separate comparison of the combined HU6 groups and placebo may be conducted.

Responder status (n, %) at Day 61 will be presented. A subject will be deemed a responder if their MRI-PDFF showed a 30% or more reduction from baseline at Day 61. Additional exploratory analysis may be performed such as a different threshold then the 30% or more reduction from baseline due to the short duration of the study.

The above summary statistics, an ANCOVA model including treatment group and the baseline score of the response variable as fixed effects, and the responder status will also be presented for the subjects randomized only to the HbA1c between 5.7% and 9.0% subgroup.

All MRI-PDFF results will be displayed in subject listings.

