12.2 Sample Size Determination

A sample size of 17 subjects per group provides at least 80% power to detect a 30% difference in the mean relative change from baseline in liver fat content at Day 61, when the standard deviation is 30% [PASS 2020: Two sample t-test, alpha=.05]. Assuming a 15% dropout rate, up to 80 subjects should be enrolled to ensure that at least 68 subjects, 17 per group, are evaluable for the primary efficacy endpoint analysis.

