12.3.2 Efficacy Analysis

The primary efficacy endpoint is the reduction in liver fat content measured by the relative change from baseline, as assessed by MRI-PDFF at Day 61. The hypothesis of interest are 2-sided tests comparing each active HU6 treatment groups to the placebo.

 $\begin{aligned} H_{01}: \mu_{placebo} &= \mu_{HU6\ 170mg} \text{vs} \ H_{11}: \mu_{placebo} \neq \mu_{HU6\ 170mg} \\ H_{02}: \mu_{placebo} &= \mu_{HU6\ 340mg} \text{vs} \ H_{12}: \mu_{placebo} \neq \mu_{HU6\ 340mg} \end{aligned}$

 $H_{03}: \mu_{placebo} = \mu_{HU6\ 510mg} \text{vs}\ H_{13}: \mu_{placebo} \neq \mu_{HU6\ 510mg}$

Relative change from baseline in liver fat content, will be analyzed for the FAS using an analysis of variance (ANCOVA) model, including treatment group, HbA_{1c} stratification (normal range versus between 5.7% and 9.0% inclusive) and baseline liver fat from MRI-PDFF as fixed effects. This estimand will include available MRI-PDFF evaluations that occur before discontinuation of treatment. The differences between treatment groups will be based on the least square mean (LSMean) differences between each HU6 group and placebo. A separate comparison of the combined HU6 groups and placebo may be conducted. The corresponding 95% confidence interval (CI) will be presented.

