4 STUDY ENDPOINTS

4.1 Primary Endpoint

• Relative change from baseline in liver fat content, as assessed by MRI-PDFF at Day 61.

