5.3 Sample Size Justification

A sample size of 17 subjects per group provides at least 80% power to detect a 30% difference in the mean relative change from baseline in liver fat content at Day 61, when the standard deviation is 30% [PASS 2020: Two sample t-test, alpha=.05]. Assuming a 15% dropout rate, up

to 80 subjects should be enrolled to ensure that at least 68 subjects, 17 per group, are evaluable for the primary efficacy endpoint analysis.

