12 PHARMACODYNAMICS ANALYSES

For each pharmacodynamic variable, summary statistics (n, mean, standard deviation, minimum, median, and maximum) will be presented for the observed values at each time point for the FAS population, as described in Section 5.2, Summarization of Data. Summary statistics will also be presented for the change-from-baseline values to each postbaseline time point. For glycated albumin, placebo-corrected change-from-baseline values to each postbaseline time point will be presented. In these displays, baseline will be defined as the last non-missing value prior to first dose of study medication. Figures will be generated appropriate to the data output.

For pharmacodynamic variables with only a Day 61 post-baseline assessment [i.e., ELF variables, HbA_{1c}, abdominal MRI [liver volume, VAT, and SAT], and Fibroscan [Steatosis/VCTE and Fibrosis/CAP], summary statistics will be presented for the change-from-baseline values for each variable at Day 61. Placebo-corrected change-from-baseline values at Day 61 will be presented for abdominal MRI [liver volume, total visceral adipose tissue (VAT) and subcutaneous adipose tissue (SAT)], and Fibrosis/CAP. The ELF variables will be ELF score, hyaluronic acid, procollagen III amino-terminal peptide (PIIINP), and tissue inhibitor of matrix metalloproteinase 1 (TIMP-1). Figures will be generated appropriate to the data output.

For each pharmacodynamic variable with only a Day 61 post-baseline assessment, mean change from baseline will be analyzed for the FAS population using an ANCOVA model, including treatment group, HbA_{1c} stratification (normal range versus between 5.7% and 9.0% inclusive) and the baseline score of the response variable as fixed effects. The difference in LS Means for the change from baseline, corresponding 95% CIs, and P values will be provided to assess the treatment differences between placebo and each HU6 treatment group.

For the abdominal MRI liver volume and adiposity, the above summary statistics, an ANCOVA model including treatment group and the baseline score of the response variable as fixed effects, and the responder status will also be presented for the subjects randomized only to the HbA1c between 5.7% and 9.0% subgroup.

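### The SAP's primary ANCOVA and its LS-mean contrast omit the word relative and, read literally, analyse a different variable from the stated and powered primary endpoint

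*SAP*

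**What the plan says.** SAP Section 4.1 gives the primary endpoint as "Relative change from baseline in liver fat content, as assessed by MRI-PDFF at Day 61", and Protocol Section 5.2.1 says the same. SAP Section 11 opens consistently, describing the endpoint as "the reduction in liver fat content measured by the relative change from baseline, as assessed by MRI-PDFF at Day 61". The sample size is set for a "30% difference in the mean relative change from baseline in liver fat content at Day 61" with an SD of 30% (SAP Section 5.3; Protocol Section 12.2 matches). Protocol Section 12.3.2 carries this into the model: "Relative change from baseline in liver fat content, will be analyzed for the FAS using an analysis of variance (ANCOVA) model".

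The model sentence in SAP Section 11 reads differently: "Mean change from baseline in liver fat content will be analyzed for the FAS population using an analysis of covariance (ANCOVA) model". The reported contrast follows it: "The difference in LS Means for the change from baseline, corresponding 95% CIs, and P values will be provided". Neither sentence contains the word *relative*. The descriptive summaries in that section are likewise for change and placebo-corrected change. The only output there that is explicitly on a percentage scale is the responder rule (a reduction of 30% or more).

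**The concern.** The sentence that generates the primary P values names a variable that, taken at face value, is Day 61 minus baseline in PDFF points. That is neither the stated endpoint, nor the powered one, nor the protocol's ANCOVA response.

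The SAP's own usage supports the literal reading. Section 12 uses the same model wording, "mean change from baseline will be analyzed for the FAS population using an ANCOVA model", and repeats the contrast sentence word for word. There it covers endpoints that Section 4.2 defines as plain change (VAT, SAT, VCTE, CAP, ELF, HbA1c). The subgroup ANCOVA at the end of Section 11 names no response variable, so it inherits the ambiguity.

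What is at stake is which quantity is reported as the primary result. A programmer working from the model sentence would produce estimates in PDFF points that cannot be set directly against the design assumption of a 30% difference. Because the scale is left open, it could also be settled after results are known.

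**Working it through.** **1. Reproduce the stated sample size on the relative scale.** Inputs from SAP Sections 5.2 and 5.3: difference 30, SD 30, n = 17 per group, two-sided alpha 0.05, two-sample t-test, 15% dropout.

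- Noncentrality = (30/30) × √(17/2) = 2.92, with 2 × 17 − 2 = 32 degrees of freedom.
- Power = 80.7% at n = 17 and 78.1% at n = 16, so 17 is the smallest group size reaching 80%.
- Enrolment: 4 × 17 = 68, and 68/(1 − 0.15) = 80.

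Every stated figure reproduces.

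**2. Compare the model text.** Protocol Section 12.3.2 and SAP Section 11 give the same model: treatment group, HbA1c stratum and baseline PDFF, fitted in the FAS. The protocol has *Relative* where the SAP has *Mean*. The SAP revision table (Section 18) records no change of response variable.

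**3. Convert a 30% relative fall into PDFF points** (0.30 × baseline). Only the 8% entry minimum comes from the documents; the other baselines are assumed.

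| Baseline PDFF | Absolute fall |
|---|---|
| 8% (entry floor) | 2.4 points |
| 12% | 3.6 points |
| 20% | 6.0 points |
| 30% | 9.0 points |

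The 30%/30% design inputs therefore do not carry over to absolute change.

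**4. See how often the choice of scale would matter.** The SAP ANCOVA (four arms, 17 per arm) was fitted to both variables in simulated trials, 10,000 per scenario. The following assumptions are not in the documents:

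- baseline PDFF normal with (mean, SD) of (15, 4), (15, 6), (20, 5) or (20, 8), truncated to 8–40;
- HbA1c strata split 50/50;
- the same effect at all three doses;
- Day 61 PDFF floored at 0;
- effect and SD constant either on the relative scale (SD 30) or on the absolute scale, at the same percentage of the nominal mean baseline.

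This gives eight scenarios per effect size. Share of results where the two scales disagree on p<0.05:

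| True effect (relative points) | Per dose contrast | At least one of three doses |
|---|---|---|
| 0 | 2.1–3.1% | 5.9–8.6% |
| 7.5 | 3.4–5.2% | 9.5–14.1% |
| 15 | 6.3–9.8% | 17.2–25.2% |
| 22.5 | 7.5–11.2% | 20.1–28.9% |
| 30 | 5.6–8.7% | 15.3–22.5% |
| 37.5 | 2.7–4.0% | 7.4–10.8% |
| 45 | 0.6–1.4% | 1.8–3.7% |

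Without the floor at 0, the upper ends of the per-contrast ranges rise to 12.4% at 22.5, 10.0% at 30 and 2.0% at 45.

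**5. Check whether either scale is better.** At an effect of 30, power was 80.4–81.2% (relative) against 77.1–78.9% (absolute) when the effect is constant on the relative scale. It was 77.5–79.3% against 80.6–81.5% when the effect is constant on the absolute scale. In separate runs of 4,000 trials per scenario, the rejection rate at zero effect was 4.6–5.4% on both scales.

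**The case against.** The strongest reply is that the section resolves itself. It opens by defining the endpoint as relative change, the hypotheses follow directly, and this ANCOVA is the only model offered to test them. Relative change is a kind of change from baseline, the text nowhere says absolute, and every other definition in both documents says relative. On this view the shared wording in Section 12 is reused template text, and harm requires a programmer to read one sentence in isolation. The discordance rates also rest on assumed baselines, and any two imperfectly correlated tests will disagree near p = 0.05.

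Much of this stands. A drafting slip is the likeliest explanation and relative change the likelier intent. No bias, type I error or power defect has been shown, and the simulation is illustrative only. But nothing in the SAP says that change in the model sentence means relative change, and the same words elsewhere in the SAP do mean plain change. That context favours one reading is a reason to correct the sentence. It does not make the sentence adequate as the specification of the primary analysis.

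**Conclusion.** The concern holds. As worded, the SAP's primary model and contrast do not match the endpoint, the power statement or the protocol's model. The practical size is modest: the reporting scale is ambiguous, and under the assumptions above the two scales would give a different significance call in roughly 6–9% of dose contrasts at the design effect and 2–3% under no effect. Which scale has more power depends on how the effect is assumed to act, and the gap is only a few percentage points either way. No sample-size figure is affected. The textual conflict and the conversion at the 8% floor need no assumption; the discordance and power figures do. It should be fixed because it concerns the primary analysis variable, but it is not a design failure.

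**What to change.** Add to SAP Section 11: *The dependent variable of the primary ANCOVA, and of the ANCOVA in the HbA1c 5.7–9.0% subgroup, is relative change in MRI-PDFF, 100 × (Day 61 − baseline)/baseline; LS-mean differences, 95% CIs and P values are reported on that scale.* Label any absolute-change analysis as supportive.

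Two small additions would help but are not essential: a descriptive summary of relative change alongside the existing change summaries, and a note that the covariate in the subgroup model is baseline PDFF.

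The cost is one sentence. The percentage change per subject is already needed for the 30% responder rule, and 17 per group, 68 evaluable and 80 enrolled all stand.
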